8.2.4. Drug Concentration and Measurements

Samples for drug concentration measurement will be collected at visits listed in Table 1. The samples are to be collected prior to the administration of study drug. In the event of suspected SAEs, such as anaphylaxis or systemic hypersensitivity, additional samples for the analysis of REGN5713, REGN5714, and REGN5715 drug concentration may be collected as close to the event as practically possible.

8.2.5. Immunogenicity Measurements and Samples

Samples for ADA measurement will be collected at visits listed in Table 1. The samples are to be collected prior to the administration of study drug. In the event of suspected SAEs, such as anaphylaxis or systemic hypersensitivity, additional samples for the analysis of ADA may be collected as close to the event as practically possible.

8.2.6. Pharmacodynamic and Exploratory Biomarker Procedures

This section describes planned exploratory PD/biomarker analyses, some of which may be reported in the CSR. Samples will be collected at time points according to Table 1. The biomarkers studied will be those known or hypothesized to be relevant to the pathophysiology of birch allergy, mechanism of action and/or safety of REGN5713-5714-5715, REGN5713-5715, and REGN5715.

Detailed instructions for blood sample collection are included in the laboratory manual.

Any biological samples (eg, blood, serum, plasma) collected during the study, which are not used for their planned purpose, or for which material remains after their planned analysis, may be kept for up to 15 years after study completion (or for a shorter time period if required per regional laws and regulations) for use in exploratory research related to REGN5713-5714-5715, REGN5713-5715, and REGN5715 safety and/or efficacy, birch allergy and related allergies, the biology of Bet v 1 and/or for related assay development and/or validation.

8.2.6.1. Basophil Activation Test

In this study, exploratory biomarker assessments will be performed to better understand the effects of REGN5713-5714-5715, REGN5713-5715, and REGN5715 administration on biomarkers of birch allergy or relevant physiological and pathogenic processes. This will include the assessment of allergen-specific IgE levels in serum samples during the study. Additionally, whole blood may be collected and processed as per the laboratory manual for basophil responsiveness testing in the basophil activation test (BAT). If an indirect basophil activation assay is available, frozen serum samples may be tested.

Basophils are an effector cell type involved in acute allergic reactions. A BAT assay is an in vitro cellular functional test that measures basophil activation by the flow cytometric assessment of the degree of degranulation following stimulation of the sample with allergens or controls, providing an objective method to quantify the allergen-specific reactivity and sensitivity of basophils.

In a previous randomized, double-blind, placebo-controlled, 2-part phase 1 study, where in Part B, patients were administered a single dose of REGN5713-5714-5715 at 900 mg SC, it was demonstrated that treatment with REGN5713-5714-5715 significantly lowered basophil responsiveness to birch pollen extract as compared to placebo (Gevaert, 2022). A correlation between the basophil response as measured by BAT assay and the clinical symptom improvements

in TNSS and SPT was observed, indicating that the less sensitive the basophils are to birch pollen in a BAT assay, the greater the clinical benefit the patients may achieve. As such, it is possible that the inhibition of basophil/mast cell degranulation may be a key mechanism by which REGN5713-5714-5715 ameliorates the allergic symptoms downstream of birch pollen exposure. Therefore, in this study a BAT assay may be used to assess the inhibitory effect of anti-Bet v 1 antibodies (which may include but not be limited to assessments such as EC₅₀ and/or % change in EC₅₀ from baseline/pre-dose/EEU exposure) on basophil activation after ex-vivo stimulation with birch pollen and/or Bet v 1 in REGN5713-5714-5715, REGN5713-5715, and REGN5715 treated participants vs placebo. Correlations to clinical symptom measurements may also be made. A BAT assay may be performed for approximately 100 of the randomized participants (subset of the total enrolled population at one or both EEU sites; additional samples may be required at the screening visit since participants may screen fail after the EEU challenge). Assessments will be done in each of the active treatment arms versus placebo.

8.2.6.2. Nasal Fluid Collection

Nasal fluid may be collected from a subset of participants. It is recommended to collect these samples in the same participants from whom BAT samples were collected. Samples will be collected in approximately 100 randomized participants at specified visits in Table 1. At each visit, the nasal fluid samples will be collected at 2 time points, prior to the start of the EEU challenge and then at 6 hours after completion of the challenge.

Exploratory biomarker results not required for protocol-defined endpoint analyses will not be reported in the CSR. These results may be in a separate exploratory biomarker report.

8.2.7. Future Biomedical Research (Optional)

Participants who agree to participate in the future biomedical research (FBR) sub-study will be required to consent to this optional sub-study before samples are banked for FBR. Additional samples (plasma and serum) will be collected for FBR. Residual biomarker/biological samples for study-related research, as well as unused PK and ADA samples, will be stored for up to 15 years after the final date of the database lock (or for a shorter time period if required per regional laws and regulations). The samples may be utilized for FBR that may or may not be directly related to the study, including being used as reference samples and assay development or validation.

The results of these future biomedical research analyses will not be presented in the CSR.

8.2.8. Pharmacogenomic Analysis (Optional)

Participants who agree to participate in the genomics sub-study will be required to consent to this optional sub-study before collection of the samples. Whole blood samples for DNA extraction should be collected on day 1/baseline (pre-dose) but can be collected at a later study visit (Table 1). DNA samples will be collected for pharmacogenomics analyses to understand the genetic determinants of efficacy and safety associated with the treatments in this study and the molecular basis of birch allergy and related diseases. These samples will be single-coded as defined by the International Council for Harmonisation (ICH) guideline E15. Samples will be stored for up to 15 years after the final date of the database lock (or for a shorter time period if required per regional laws and regulations). If there are specific site or country requirements involving the

pharmacogenomic analyses which the sponsor is unable to comply with, samples will not be collected at those sites.

The purpose of the pharmacogenomic analyses is to identify genomic associations with clinical or biomarker response to REGN5713-5714-5715, other birch allergy clinical outcome measures and possible AEs. In addition, associations between genomic variants and prognosis or progression of birch allergy as well as related allergic diseases may also be studied. These data may be used or combined with data collected from other studies to identify and validate genomic markers related to the study drug, target pathway, or birch allergy and related diseases.

Analyses may include sequence determination or single nucleotide polymorphism studies of candidate genes and surrounding genomic regions. Other methods, including whole-exome sequencing, whole-genome sequencing, and DNA copy number variation may also be performed. The list of methods may be expanded to include novel methodology that may be developed during the course of this study or sample storage period. Results from the genomic analyses will not be reported in the CSR.

9. SAFETY EVALUATION AND REPORTING

9.1. Recording and Reporting Adverse Events

9.1.1. General Guidelines

The investigator must promptly record all clinical events occurring during the study data collection, from the time of signing the informed consent form (ICF) to the end of on-treatment period (see Section 10.4.5.1). Medical conditions that existed or were diagnosed prior to the signing of the informed consent will be recorded as part of medical history. Abnormal laboratory values and vital signs observed at the time of informed consent should also be recorded as medical history. Any subsequent worsening (ie, any clinically significant change in frequency and/or intensity) of a pre-existing condition that is temporally associated with the use of the study drug should also be recorded as an AE.

At each visit, the investigator will determine whether any AEs have occurred by evaluating the participant. Adverse events may be directly observed, reported spontaneously by the participant, or by questioning the participant at each study visit. Participants should be questioned in a general way, without asking about the occurrence of any specific symptoms. The Investigator must assess all AEs to determine seriousness, severity, and causality, in accordance with the definitions in Section 9.2. The Investigator's assessment must be clearly documented in the site's source documentation with the Investigator's signature. The Investigator should follow up on SAEs (and AESIs) until they have resolved or are considered clinically stable; AEs should be followed until they are resolved or last study visit, whichever comes first.

Although not considered an adverse event, if a pregnancy occurs during the study, information about the progress and outcome of the pregnancy will be collected. This should include the date that the participant became pregnant, information about the health of the participant, any medication treatments received during the pregnancy, any medical problems affecting or related to the pregnancy and/or the baby, whether the pregnancy came to term, the date of the child's birth, and the health of the child after birth. To collect this information, the study staff should contact the participant every trimester for updates on the pregnancy. The participant should also be asked to contact the site as soon as possible in the event of any medical problem affecting or related to the pregnancy and/or baby. Once the baby is born, the study staff will ask for a final update after one well-baby visit with the pediatrician.

Always report the diagnosis as the AE or SAE term. When a diagnosis is unavailable, report the primary sign or symptom as the AE or SAE term with additional details included in the narrative until the diagnosis becomes available. If the signs and symptoms are distinct and do not suggest a common diagnosis, report them as individual entries of AE or SAE.

Laboratory results, vital signs, and other diagnostic results or findings should be appraised by the Investigator to determine their clinical significance. Isolated abnormal laboratory results, vital sign findings, or other diagnostic findings (ie, not part of a reported diagnosis) should be reported as AEs if they are symptomatic, lead to study drug discontinuation, dose reduction, require corrective treatment, or constitute an AE in the investigator's clinical judgment.

For events that are serious due to hospitalization, the reason for hospitalization must be reported as the SAE (diagnosis or symptom requiring hospitalization). A procedure is not an AE or SAE, but the reason for the procedure may be an AE or SAE. Pre-planned (prior to signing the ICF) procedures, treatments requiring hospitalization for pre-existing conditions that do not worsen in severity, and admission for palliative or social care should not be reported as SAEs (see Section 9.2 for Definitions).

For deaths, the underlying or immediate cause of death should always be reported as an SAE.

Any SAE that may occur subsequent to the reporting period (end of the on-treatment period) that the Investigator assesses as related to study drug should also be reported.

All AEs, SAEs, AESIs, and pregnancy reports are to be reported according to the procedures in Section 9.1.3.

9.1.2. Reporting Procedure

All events (serious and non-serious) must be reported with investigator's assessment of the event's seriousness, severity, and causality to the (when applicable: blinded) study drug. For SAEs and AESIs, a detailed narrative summarizing the course of the event, including its evaluation, treatment, and outcome should be provided on the AE case report form (CRF). Specific or estimated dates of event onset, treatment, and resolution should be included, when available. Medical history, concomitant medications, and laboratory data that are relevant to the event should also be summarized in the narrative. For fatal events, the narrative should state whether an autopsy was or will be performed, and include the results if available. Information not available at the time of the initial report must be documented in a follow-up report. Source documents (including hospital or medical records, diagnostic reports, etc) will be summarized in the narrative on the AE CRF, and retained at the study center and available upon request.

Urgent safety queries must be followed up and addressed promptly. Follow-up information and response to non-urgent safety queries should be combined for reporting to provide the most complete data possible within each follow-up.

The investigator (or designee) will record all AEs that occur from the time the informed consent is signed until the end of study with the exception of allergic symptoms that occur in response to the EEU challenge within 24 hours following the EEU. Allergic symptoms that occur in response to the EEU are not to be reported as AEs, as they will be recorded as outcome measures. However, AEs that occur in response to allergen exposure in the EEU that are outside of expected symptoms, including events which qualify as SAEs, up to 24 hours after EEU session, should be reported as AEs and SAEs, as applicable.

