7.2. Rescue Treatments

For all EEU challenges and in study **Part B**, participants will be provided with the following allergy-relieving rescue medications (or appropriate in-class equivalent, after agreement with sponsor) to treat allergic symptoms as needed during the study:

- 1. oral desloratadine 5 mg (second generation antihistamine)
- 2. topical olopatadine 1 mg/mL (antihistamine eye drops)
- 3. topical mometasone furoate 50 μg/dose (INCS)

During specified periods, including Part B of the study, participants will be asked to record their daily medication use using an e-diary, including the name and amount of these pre-specified medications.

For EEU Exposure(s) and Skin Prick Testing

Allergen exposure can induce immediate or late allergic reactions, such as allergic conjunctivitis, allergic rhinitis, asthma symptoms, or rarely anaphylaxis, in sensitized participants, which will be treated appropriately at the discretion of the investigator. With the exception of severe or clinically concerning reactions (as judged by the investigator), rescue treatments, as needed, can be dispensed after study endpoint data collection is obtained (eg, after EEU challenge data are collected, after the skin wheals are measured after application of allergen during skin prick testing).

During the study, participants will be asked to refrain from taking specific prohibited medications, including as specified within the time period preceding screening and EEU visits (Section 7.9.1).

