- 7. Part A EEU challenges: TNSS and TOSS are recorded using an e-diary at baseline and then every ~20 minutes while in the EEU, then continued ~ every 2 hours until ~24 hours after the start of the EEU exposure (except during sleep). After completion of the EEU challenges, use of allergy medicines will be recorded in the e-diary until ~24 hours after the start of the EEU challenges. An assessment of TNSS is performed once prior to the start of the EEU exposure at visits 2, 3, 6, 7, 8, 9. If TNSS ≤2, then the visit activities can proceed. If TNSS is >2, then the visit can be rescheduled within the window. Washouts for medications prior to EEU visits are specified in prohibited medications (Section 7.9.1).
- 8. Part B EEU challenges: There are no TNSS thresholds for the peak birch pollen season EEU visit (visit 13). The birch EEU challenge at the end of the season (visit 14) may not be performed in grass-allergic participants who are highly symptomatic or unable to wash out allergy relieving rescue medications due to grass pollen allergy symptoms, per PI discretion.

- 9. On a case-by-case basis, an EEU challenge visit window post-randomization may be extended up to +14 days for any illnesses (eg, respiratory illness, common cold, etc) that may potentially confound the assessments and/or potentially impact participant safety, per PI discretion in consultation with the sponsor.
- 10. Randomization may occur within 1 day prior to study drug administration.
- 11. In Part B, participants who received either 3-mAb, 2-mAb, 1-mAb, or placebo in Part A will continue the same treatment in Part B.
- 12. Dosing window for visit 11 is within approximately 0 to 3 weeks prior to start of the anticipated BPS.
- 13. Visit timeframes in Part B (visits 10 to 15) may vary based on the timing and duration of the anticipated BPS. End-of-season EEU challenge (visit 14) should occur after the end of the protocol-defined end of the BPS.
- 14. Dose #2 should be administered at minimum 12 weeks after dose #1.
- 15. Participants will be contacted within 1 day (visit 12) after dose 2 (visit 11) via telephone to monitor safety trends.

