7. EFFICACY/PHARMACODYNAMIC DATA

7.1. Description of Efficacy/Pharmacodynamic Data

EEU Data (symptom scores recorded during the 6 hour EEU challenges):

Nasal and ocular symptom data will be collected during EEU visits that occur during the screening period, out-of-season efficacy period, in-season efficacy period, and at end-of-season. The methodology for collecting and scoring the nasal and ocular symptom data in the EEU is consistent across all periods stated previously.

• TNSS (2 to 6 hours):

Instantaneous TNSS measures nasal symptom severity at the time point of assessment. In the EEU, instantaneous TNSS is recorded using an e-diary prior to start of pollen exposure and then approximately every 20 min during the 6-hour EEU pollen exposure.

The instantaneous TNSS score ranges from 0 to 12 and is based on assessment of 4 nasal symptoms graded on a Likert scale ranging from 0 (none) to 3 (severe) for nasal congestion, itching, and runny nose, and sneezing. Higher score indicates worse symptoms.

The mean TNSS (2-6 hours) is calculated as an average of the observed instantaneous TNSS scores during the 12 timepoints from hour 2 to 6 during the EEU session (details in Section 11.4).

• TOSS (2 to 6 hours):

Instantaneous TOSS measures ocular symptom severity at the time point of assessment. In the EEU, instantaneous TOSS is recorded using an e-diary prior to start of pollen exposure and then approximately every 20 min during the 6-hour EEU pollen exposure.

The intantaenous TOSS score ranges from 0 to 6 and is based on 2 groups of eye symptoms: itching/redness/gritty feeling and tearing/watering. Each of the 2 symptom groups is graded on a Likert scale ranging from 0 (none) to 3 (severe). Higher score indicates worse symptoms.

The mean TOSS (2-6 hours) is calculated as an average of the observed instantaneous TOSS scores during the 12 timepoints from hour 2 to 6 during the EEU session (details in Section 11.4).

• TSS (2 to 6 hours) (calculated):

The mean TSS (2 to 6 hours) is calculated as an average of the sum of observed instantaneous TNSS and instantaneous TOSS scores during the 12 timepoints from hour 2 to 6 during the EEU session (details in Section 11.4). The mean TSS (2 to 6 hours) score ranges from 0 to 18 with higher scores indicating worse symptoms.

Note: Baseline data are obtained from the screening baseline EEU challenge for birch (visit 2) and oak (visit 3).

Daily scores:

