7.2.1.1. Estimand Framework for the Primary Endpoint

The intercurrent events, strategies, and the corresponding missing data handling approaches for the primary estimands of interest for the primary endpoint are provided in detail in Table 2. Day 29 EEU data during out-of-birch pollen season are planned to assess in the protocol amendment #1 dated November 2022. However, some randomized participants are not eligible to complete EEU Day 29 challenges due to early start of the pollen season. The pollen season occurring before Day 29 is identified as an intercurrent event for the study primary objective. The corresponding estimand framework is used by hypothetical setting not to collect EEU data at Day 29 (all values during EEU Visit 6 are missing). In cases where EEU assessments at Day 29 are collected after the pollen season, these collected EEU data will be set to missing (hypothetical strategy).

Table 2: Summary of Estimand for Primary Endpoint

	Estimand			
Endpoint Category	Endpoint	Population	Intercurrent event(s) handling strategy and missing data handling	Population- level summary
Primary endpoint – Continuous	Mean Total Nasal Symptom Score (TNSS) (2 to 6 hours) in a birch allergen EEU at day 29 in Part A	FAS	 Relevant prohibited medication¹ taken prior to the EEU challenge: all available data will be utilized (treatment policy). Any severe or clinically concerning adverse event necessitating removal from the chamber and/or use of rescue treatment² taken during the EEU challenge: data after exiting the EEU or the use of the rescue medication will be set to mean TNSS from 2 to 6 hours in the baseline EEU (BOCF, composite strategy) In addition, if all values during the EEU visit are missing due to any other reason, e.g., early start of BPS, then the averaged value will be imputed using multiple imputation (MI). 	ANCOVA model with treatment group and stratification factors as fixed effect and the baseline mean TNSS (2 to 6 hours) at visit 2 as a covariate.

^[1] Relevant prohibited medications include allergy relieving medications (treatment policy); no participants used systemic steroids, biologics or immune therapeutics or allergen specific immunotherapy that are expected to impact type 2 allergic disease prior to completion of expected out-of-season EEU visits.

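### The AE exemption for chamber-induced allergic symptoms is wider than the outcome scores meant to replace it, so some non-serious reactions may go unrecorded

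*Protocol*

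**What the plan says.** Protocol Section 9.1.2 sets the rule. AEs are recorded from consent to end of study, "with the exception of allergic symptoms that occur in response to the EEU challenge within 24 hours following the EEU". The reason follows: "Allergic symptoms that occur in response to the EEU are not to be reported as AEs, as they will be recorded as outcome measures". That second sentence carries no time limit.

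The same paragraph then takes part of the exemption back. It refers to "AEs that occur in response to allergen exposure in the EEU that are outside of expected symptoms", includes events that qualify as SAEs, and says that these, "up to 24 hours after EEU session, should be reported as AEs and SAEs, as applicable". Section 9.1.3 separately keeps SAEs, and systemic or severe hypersensitivity whether serious or not, reportable to the sponsor.

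The challenge outcomes are described elsewhere:
- TNSS has four nasal items (Protocol 8.2.2.1) and TOSS has two eye items (Protocol 8.2.2.2).
- SAP Section 7.1 has them scored "approximately every 20 min during the 6-hour EEU pollen exposure".
- Footnote 7 of the Schedule of Events adds that scoring is "then continued ~ every 2 hours until ~24 hours after the start of the EEU exposure", with a pause for sleep.
- The separate daily diary runs only during screening and from visit 10 to visit 15 (footnote 24).

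Two further passages bear on the scope. Protocol Section 7.2 states: "Allergen exposure can induce immediate or late allergic reactions, such as allergic conjunctivitis, allergic rhinitis, asthma symptoms, or rarely anaphylaxis". SAP Table 2 lists, as an intercurrent event for the primary endpoint, "Any severe or clinically concerning adverse event necessitating removal from the chamber" and/or in-chamber rescue.

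**The concern.** Exempting a symptom from AE recording because it is scored elsewhere is sound only as far as the scoring reaches. Here the exempt category is allergic symptoms, while the scores cover the nose and the eyes. Cough, wheeze, chest tightness, throat symptoms and skin symptoms have no item. The carve-back could close the gap, but it turns on a term that the protocol never defines.

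The symptoms at issue matter to this trial. Exclusion 9 bars people whose asthma symptoms needed intervention in the screening chamber. Exclusion 7 admits people with asthma who need only an intermittent short-acting bronchodilator. After randomization the other routes by which a mild lower-airway reaction might surface are weak:
- Spirometry or peak flow at later visits is at the investigator's judgement (footnote 23).
- AE questioning is general and does not ask about particular symptoms (Section 9.1.1).
- Patient-reported outcome data are not reconciled against AEs (Section 9.2.1).

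At stake is how complete the record of non-serious challenge reactions is, and whether the two EEU locations record them alike.

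**Working it through.** No power, alpha or sample-size figure is involved. The check sets the passages against each other and does the clock arithmetic.

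**1. Which symptoms are covered**

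| Symptom after a challenge | TNSS/TOSS item? | AE under 9.1.2? |
|---|---|---|
| Nasal (4 items) | Yes | Exempt |
| Eye (2 items) | Yes | Exempt |
| Asthma, throat or skin, non-serious and non-severe | No | Depends on the meaning of *expected symptoms* |
| SAE; systemic or severe hypersensitivity | No | Reportable (9.1.2, 9.1.3) |

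The third row is the defect. If a site reads Section 7.2 as a list of what exposure is expected to cause, asthma symptoms are allergic and expected, so they are exempt and appear nowhere. If a site reads *expected* as the scored symptoms, they are AEs. The text allows both.

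**2. The two clocks, in hours from the start of exposure**

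- Session length: 6 h (SAP 7.1).
- End of challenge diary: about 24 h (footnote 7).
- End of exemption, counted from the end of the session: 6 + 24 = 30 h.
- Difference: 30 − 24 = about 6 h, that is, hours 24 to 30.
- End of exemption, counted from the start of exposure: 24 h. Difference: 24 − 24 = 0 h.

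The carve-back counts its own 24 hours after the session, which supports the 30-hour reading. The 6 hours begin 24 − 6 = 18 h after the participant leaves the chamber.

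**3. Where those 6 hours are uncovered**

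- *Screening:* the daily diary starts after the screening birch challenge in eligible participants (footnote 25), so it can pick up these hours.
- *Part B (visits 13 and 14):* the daily diary runs and asks each evening about the past 24 hours, so nasal and eye symptoms in these hours are recorded. The SAP leaves the day of a challenge and the day after out of the field averages, but the entries exist.
- *Part A after randomization (visits 6, 7, 8, 9):* the daily diary is generally not running. This is where the gap sits.

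Upper bound: 4 challenges × 300 participants = 1,200 sessions. The real number is lower. Visit 7 is for oak-allergic participants only (SAP 7.1.2), visits 8 and 9 may be skipped (footnote 40; SAP 2.1), and visit 10, which starts the daily diary, may come before Part A is finished for some participants (SAP 2.1).

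**4. Link to the SAP**

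Table 2 calls a severe or clinically concerning reaction that ends a chamber session an adverse event. Protocol 9.1.2 does not say plainly that such a reaction is outside the exemption. Any treatment given is recorded as concomitant medication (Protocol 7.9), so in-chamber rescue leaves a record whether or not an AE is entered. The wording is clearly misaligned only for chamber exit without rescue.

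**The case against.** The strongest reply is that Section 9.1.2 limits itself. It exempts symptoms because they are recorded as outcomes, so a symptom with no outcome item falls outside the reason and stays reportable. Section 7.2 concerns treatment of reactions, not AE definitions. If its list meant *expected symptoms*, anaphylaxis would be exempt too, which Section 9.1.3 rules out. This is a fair reading and probably the intended one. But it has to be inferred, and a site that applies the exemption sentence literally could reach the other result. What stands is that non-recording is possible, not certain.

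Four stronger conclusions are tempting, and the documents do not support them:

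- *Asthma and similar reactions are captured nowhere.* The carve-back and Section 9.1.3 keep unexpected, serious, and systemic or severe reactions reportable.
- *The 6-hour gap applies to every challenge.* Counting visits 13 and 14 would give 6 × 300 = 1,800 sessions, but the daily diary covers those hours in Part B.
- *The primary endpoint is at risk.* It is mean TNSS over hours 2 to 6, well inside the scored window. Rescue use is recorded independently of AEs, and loss of the Table 2 trigger is not shown.
- *The comparison between arms is biased.* Sites and participants are blinded and randomization is stratified by EEU site. Different site readings affect completeness, and no mechanism is shown by which they would favour an arm.

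It is also fair that the diary times are approximate, and that what is lost in hours 24 to 30 is late, non-serious nasal and eye symptoms.

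**Conclusion.** The point holds as a gap in safety recording. The exemption rests on alternative capture that is narrower than the exemption in two ways:

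- **Scope.** Non-serious, non-severe reactions outside the nose and eyes may be recorded neither as AEs nor as outcomes. This depends on how each site reads an undefined term. The documents give no expected event rate, so the number of reactions affected cannot be estimated.
- **Timing.** About 6 hours of nasal and eye symptoms are uncovered, mainly at visits 6 to 9, in at most 1,200 sessions. This assumes that the exemption is counted from the end of a 6-hour session. On the other reading the gap is zero.

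The consequence is limited to the completeness of non-serious safety data and its consistency across sites. It is a cheap improvement worth making.

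**What to change.** In Protocol Section 9.1.2:

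1. Limit the exemption to symptoms that are items of TNSS or TOSS.
2. Use the diary window of footnote 7 as its clock, from the start of exposure to about 24 hours after that start.
3. State that any other symptom, and any reaction leading to chamber exit or in-chamber rescue, is recorded as an AE with causality to the procedure. Section 9.2.5 already provides that category, and the third item brings the protocol into line with SAP Table 2.

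The cost is one paragraph of protocol text and site training. More mild procedure-related AEs will appear in the listings, but the procedure-causality field separates them from drug-related events. The change concerns recording only and leaves the management of reactions as it is. It cannot recover reactions from challenges already held. For those, the study report can state how each site applied the rule.
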